7.5.2 NON-RELAPSE MORTALITY (NRM)

The time from randomization until NRM will be described in the ITT population graphically for each treatment arm using the Aalen-Johansen estimator (Aalen and Johansen 1978), with numbers of subjects at risk at specific time points presented for each treatment group

and relapse/progression of the primary disease treated as a competing risk. Estimates of the cumulative incidence of NRM will be provided at 6 and 12 months post-randomization along with 95% CIs computed using the complementary log-log transformation. Gray's test will be used to compare the cumulative incidence of NRM within 12 months post-randomization between arms as the primary analysis. The estimand for NRM is presented in **Table 20**. The clinical question of interest is: what is the difference in cumulative incidence of NRM between AAT combined with corticosteroids versus PTM combined with corticosteroids in patients with high risk acute GVHD following allogeneic HSCT, regardless of discontinuation of study treatment?

Table 20: Estimand for Non-relapse Mortality

Estimand Attribute	Definition		
Variable	Non-relapse Mortality, refer to Sections 6.3.2 and 7.9 for details		
Treatment	AAT(+corticosteroids) or PTM (+corticosteroids), refer to Section 2.1 for details		
Population	Patients with high risk acute GVHD following allogeneic HSCT		
Intercurrent Events	Event	Strategy	Description
	1. Death	Composite strategy	Classified as an event
	2. Relapse / progression	Composite strategy	Classified as a non-event (competing risk)
	3. Discontinuation of study treatment	Treatment policy	No effect on variable
Population-level Summary	Cumulative incidence of NRM at 6 and 12 months with 95% CIs for each arm; Gray's test p-value comparing arms from randomization to 12 months post-randomization		

In a supplementary analysis, a Cox proportional hazards model with mixed effects will be used to compare the cause-specific hazards of NRM between treatment arms while adjusting for an MN risk fixed effect and center-group lognormal frailties. The Cox regression model will be used to evaluate the adjusted hazard ratio of treatment (AAT vs. PTM) using a point estimate and a 95% CI.

7.5.3 OVERALL SURVIVAL (OS)

The time from randomization until death from any cause will be described in the ITT population graphically for each treatment arm using the Kaplan-Meier estimator, with numbers of subjects at risk at specific time points presented for each treatment group.

Estimates of OS at 6 and 12 months post-randomization will be provided along with 95% CIs computed using the complementary log-log transformation as detailed in Kalbfleisch and Prentice 1980. For the primary analysis, the log-rank test will be used to compare OS within 12 months of randomization between arms as the primary analysis. The estimand for OS is shown in **Table 21**. The clinical question of interest is: what is the difference in overall survival between AAT combined with corticosteroids versus PTM combined with corticosteroids in patients with high risk acute GVHD following allogeneic HSCT, regardless of discontinuation of study treatment?

Table 21: Estimand for Overall Survival

Estimand Attribute	Definition		
Variable	Overall Survival, refer to Sections 6.3.3 and 7.9 for details		
Treatment	AAT (+corticosteroids) or PTM (+corticosteroids), refer to Section 2.1 for details		
Population	Patients with high risk acute GVHD following allogeneic HSCT		
Intercurrent Events	Event	Strategy	Description
	1. Death	Composite strategy	Classified as an event
Population-level Summary	2. Discontinuation of study treatment	Treatment policy	No effect on variable
	OS probabilities at 6 and 12 months with 95% CIs for each arm; log rank test p-value comparing arms from randomization to 12 months post-randomization		

In a supplementary analysis, a Cox proportional hazards model with mixed effects will be used to compare OS between treatment arms while adjusting for an MN risk fixed effect and center-group lognormal frailties. The Cox regression model will be used to evaluate the adjusted hazard ratio of treatment (AAT vs. PTM) using a point estimate and a 95% CI.

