5.1.2 Randomization

Following enrollment, patients will be stratified by centers and randomized within each center in a 1:1 ratio using permuted blocks of random sizes for the two treatment arms.

Treatment practices differ considerably by centers. This includes the time to declare a patient refractory to steroids and potentially initiate next-line therapy. The variability by center may produce greater differences in treatment groups compared with age (adolescent vs adult), GVHD risk or disease. Additionally, the pathobiology of GVHD in both adolescent and adult and in malignant and non-malignant disease patient populations are similar. Therefore, since the presentation of GVHD and the anticipated response to treatment are expected to be similar, center was prioritized as the primary stratification variable.

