3.6 RANDOMIZATION

Participants will be randomized at a 1:1 ratio between the AAT and PTM treatment arms using permuted blocks of random sizes. Randomization will be stratified by treatment center. Randomization will be conducted in the Suvoda IRT system after enrollment has been completed in Advantage eClinical.

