2. Duration of Response, Primary Definition: The log-rank test for comparing the DOR from Day 28 to 12 months post-randomization from the primary analysis as specified in **Section 7.5.1** (two-sided at 5% level)
3. Duration of Response, Supplementary Definition: The log-rank test for comparing the DOR from Day 28 to 12 months post-randomization from the supplementary analysis as specified in **Section 7.5.1** (two-sided at 5% level)
4. Non-relapse Mortality: The Gray's test for comparing the cumulative incidence of NRM from randomization to 12 months post-randomization as specified in **Section 7.5.2** (two-sided at 5% level)
5. Overall Survival: The log-rank test for comparing the OS from randomization to 12 months post-randomization from the primary analysis as specified in **Section 7.5.3** (two-sided at 5% level)

6. Progression-free Survival: The log-rank test for comparing the PFS from randomization to 12 months post-randomization from the primary analysis as specified in **Section 7.5.4** (two-sided at 5% level)
7. GVHD-free Survival at Day 56: The Wald test from the logistic mixed model as specified in **Section 7.5.5** (two-sided at 5% level)

The gatekeeping procedure evaluates the endpoints sequentially in the order displayed and ends if the one-sided test or two-sided test for an endpoint fails to find a significant result showing superiority of AAT to PTM, precluding further testing of any remaining endpoints in the hierarchy. This strategy ensures control of the one-sided familywise type I error rate at 2.5% and permits claims of confirmatory benefit for any endpoint(s) where superiority of AAT is demonstrated. Any hypothesis testing performed outside the hierarchy is deemed descriptive in this study.

Analyses for several endpoints involve adjustment for center effects through regression modeling. Because the average number of patients enrolled per center is expected to be small ($136/25 \approx 5.5$), centers will be combined into center-groups for these analyses to ensure the stability of the models. This will be done by including the top 5 enrolling centers each as a separate group and combining all other centers into a sixth catchall group.

All efficacy analyses will be conducted using the ITT population unless otherwise specified.

Table 14: Endpoints for Analysis Under Each Analysis Population

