7.4.1 ANALYSIS STRATEGY

The primary objective of this study is to evaluate whether AAT treatment provides a superior Day 28 overall response (CR+PR) rate in contrast to placebo-to-match (PTM). The overall response rate is suspected to differ by treatment center and Minnesota (MN) risk category (high vs. standard). Because the average number of patients enrolled per center is

expected to be small ($136/25 \approx 5.5$), centers will be combined into center-groups for these analyses to ensure the stability of the models. This will be done by including the top 5 enrolling centers each as a separate group and combining all other centers into a sixth catchall group.

A logistic mixed model will be used to evaluate the effect of study treatment on Day 28 overall response while accounting for these factors, with center-group included as a random effect and treatment arm (AAT vs. PTM) and MN risk as fixed effects.

The primary hypothesis is that the Day 28 overall response rate under AAT treatment exceeds this proportion under PTM after adjusting for center and MN risk. No interactions of center or MN risk with treatment assignments are expected. Therefore, the null and alternative hypotheses for this comparison are:

- H_0 : Adjusted odds ratio of response for AAT vs. PTM ≤ 1
- H_A : Adjusted odds ratio of response for AAT vs. PTM > 1

This odds ratio will be evaluated in the logistic mixed model using a one-sided, group sequential test with an overall type I error rate controlled at 2.5%. The standardized log odds ratio estimate from this model will be used as the test statistic (Z-statistic) at each stage. Positive values of the Z-statistic correspond to higher estimated odds of overall response for the AAT group compared to PTM.

Sequential testing of the treatment effect of AAT relative to PTM will be performed using a two-stage design with one interim analysis for futility based on a Gamma family error spending function from Hwang et al. 1990 with $\gamma = -8$. The interim futility analysis will occur after 76 patients are evaluable for Day 28 response and the final analysis will happen after the total study population becomes evaluable.

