7.5 ANALYSIS OF SECONDARY ENDPOINTS

7.5.1 DURATION OF RESPONSE (DOR)

DOR will be evaluated in the set of patients in the ITT population who achieve a response (CR/PR) at Day 28. DOR will be estimated using the Kaplan-Meier estimator, with the probability of having a durable response, i.e. retaining the CR/PR, evaluated at 6 and 12 months post-randomization. Estimates and 95% CIs for the median and quartiles of the DOR will be obtained from the Kaplan-Meier estimator using the inverse Kaplan-Meier method described in Andersen et al. 1993. DOR will be compared from Day 28 to 12 months post-randomization between arms using a log rank test. DOR will also be displayed graphically using Kaplan-Meier curves with numbers of subjects at risk at specific time points presented for each treatment group.

Primary and supplementary analyses will be performed. In the primary analysis, DOR is defined as stated in section 6.3.1, as the time from Day 28 response to progression of acute GVHD, any next-line GVHD therapy, escalation of prednisone-equivalent steroid dose to 2.5mg/kg/day or more, or death from any cause. Its estimand is displayed in **Table 18**. The clinical question of interest is: what is the difference in duration of response between AAT combined with corticosteroids versus PTM combined with corticosteroids in patients with high risk acute GVHD following allogeneic HSCT who attain a Day 28 overall response, regardless of discontinuation of study treatment?

Table 18: Estimand for Duration of Response - Primary Analysis

Estimand Attribute	Definition		
Variable	Duration of Response; refer to Sections 6.3.1 and 7.9, and above for details		
Treatment	AAT (+corticosteroids) or PTM (+corticosteroids), refer to Section 2.1 for details		
Population	Patients with high risk acute GVHD following allogeneic HSCT who attain a Day 28 overall response		
Intercurrent Events	Event	Strategy	Description

Estimand Attribute	Definition		
	1. Acute GVHD progression	Composite strategy	Classified as an event
	2. Death	Composite strategy	Classified as an event
	3. Initiation of additional systemic aGVHD treatment ¹	Composite strategy	Classified as an event
	4. Discontinuation of study treatment	Treatment policy	No effect on variable
Population-level Summary	Median and quartiles with 95% CIs for each arm; probabilities of durable response at 6 and 12 months by arm; log rank test p-value comparing arms from Day 28 to 12 months post-randomization		

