7.5.4 PROGRESSION-FREE SURVIVAL (PFS)

PFS is defined as being alive and free of relapse/progression of the primary disease. The time from randomization until PFS failure will be described in the ITT population graphically for each treatment arm using the Kaplan-Meier estimator, with numbers of subjects at risk at specific time points presented for each treatment group. Estimates of PFS at 6 and 12 months post-randomization will be provided along with 95% CIs computed using the complementary log-log transformation as detailed in Kalbfleisch and Prentice 1980. For the primary analysis, the log-rank test will be used to compare PFS within 12 months post-randomization between arms as the primary analysis. **Table 22** shows the estimand for PFS. The clinical question of interest is: what is the difference in PFS between AAT combined with corticosteroids versus PTM combined with corticosteroids in patients with high risk acute GVHD following allogeneic HSCT, regardless of discontinuation of study treatment?

Table 22: Estimand for Progression-free Survival

Estimand Attribute	Definition		
Variable	Progression-free Survival, refer to Sections 6.3.4 and 7.9 for details		
Treatment	AAT (+corticosteroids) or PTM (+corticosteroids), refer to Section 2.1 for details		
Population	Patients with high risk acute GVHD following allogeneic HSCT		
Intercurrent Events	Event	Strategy	Description
	1. Death	Composite strategy	Classified as an event
	2. Relapse / progression	Composite strategy	Classified as an event
	3. Discontinuation of study treatment	Treatment policy	No effect on variable

Estimand Attribute	Definition
Population-level Summary	PFS probabilities at 6 and 12 months with CIs for each arm; log rank test p-value comparing arms from randomization to 12 months post-randomization

In a supplementary analysis, a Cox proportional hazards model with mixed effects will be used to compare PFS between treatment arms while adjusting for an MN risk fixed effect and center-group lognormal frailties. The Cox regression model will be used to evaluate the adjusted hazard ratio of treatment (AAT vs. PTM) using a point estimate and a 95% CI.

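### Should the confirmatory tests of non-relapse mortality, overall survival and progression-free survival be stratified by Minnesota risk?

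*SAP*

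**What the plan says.** SAP 7.1 sets a seven-step gatekeeping hierarchy. The steps in question are 4 to 6:

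- Step 4, NRM (SAP 7.5.2): "Gray's test will be used to compare the cumulative incidence of NRM within 12 months post-randomization between arms as the primary analysis".
- Step 5, overall survival (SAP 7.5.3): "the log-rank test will be used to compare OS within 12 months of randomization between arms as the primary analysis".
- Step 6, PFS (SAP 7.5.4): "the log-rank test will be used to compare PFS within 12 months post-randomization between arms as the primary analysis".

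None of these names a stratum. Protocol 5.7.2 and 5.7.3 name the same tests, also without strata. For each endpoint the SAP adds a supplementary mixed-effects Cox model with Minnesota risk as a covariate and a center-group frailty. SAP 7.1 limits the standing of such extra tests: "Any hypothesis testing performed outside the hierarchy is deemed descriptive in this study".

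Step 1, Day 28 response, uses a logistic mixed model "with center-group included as a random effect and treatment arm (AAT vs. PTM) and MN risk as fixed effects". Step 7, GVHD-free survival, is adjusted in the same way. Steps 2 and 3, duration of response, are unadjusted: "DOR will be compared from Day 28 to 12 months post-randomization between arms using a log rank test".

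On allocation, SAP 3.6 says "Randomization will be stratified by treatment center". Protocol 5.1.2 gives the reason and concludes that "center was prioritized as the primary stratification variable".

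**The concern.** Minnesota risk is known for every patient at entry, because it separates eligibility groups A and B. Protocol 1.3.1 reports that it predicts 6-month NRM (22% standard against 44% high risk). With 68 patients per arm and no balancing on risk, the arms can differ on it by chance. The hierarchy adjusts for risk in steps 1 and 7 but not in the three mortality-related steps between them, and the Cox models that do adjust are only descriptive.

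The worry is that a confirmatory survival result could be moved by chance imbalance. A real effect could be missed when AAT receives more high-risk patients, and a claim could be open to challenge when it receives fewer. A two-stratum test looks like a nearly free remedy.

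**Working it through.** **1. The plan's own figure.** The only sizing is for Day 28 response: 50% against 75%, 68 per arm, one-sided 2.5%, stated power 86%. It reproduces at 86.2%, both by formula and with the futility look. No event count, hazard ratio or power is given for NRM, survival or PFS, so those inputs are assumptions below.

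**2. How prognostic is risk among patients this trial enrolls?** Pool 6-month NRM in Protocol Table 1-1 as sum(n × rate) / sum(n).

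- Eligible standard-risk rows: (14×0.29 + 19×0.33 + 9×0.44 + 30×0.30)/72 = 23.29/72 = 32.3%.
- High-risk lower-GI rows: 61.98/145 = 42.7%.
- Difference 10.4 points. SE = √(0.323×0.677/72 + 0.427×0.573/145) = 6.9 points, so the approximate 95% CI is -3 to 24.
- Hazard ratio = ln(1-0.4274)/ln(1-0.3235) = 1.43, 95% CI 0.88 to 2.31.
- Without the liver rows: (61.98-24.01)/(145-46) = 37.97/99 = 38.4%, hazard ratio 1.24.
- General cohort, 22% against 44%: ln(0.56)/ln(0.78) = 2.33. This is an upper bound, because its standard-risk group is all standard-risk patients. The trial admits only two standard-risk presentations, which SAP 4.1 regards as close to high risk on Day 28 response.

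**3. How often are the arms unbalanced?** With a 35% or 65% high-risk share, the SD of the between-arm difference is √(2×0.35×0.65/68) = 8.2 points. In simulation, a difference of 10 points or more occurs in about 12% of trials in each direction.

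**4. Power for overall survival.** Assumptions: 40,000 trials per scenario, exponential times, censoring at day 365, treatment hazard ratio 0.6 on non-relapse deaths, 10% relapse deaths by 12 months, Table 1-1 rates. Each cell is unstratified / stratified power.

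| Trials | 35% high risk | 65% high risk |
|---|---|---|
| All | 47.6 / 47.8 | 50.7 / 50.8 |
| Imbalance ≥10 points against AAT | 39.7 / 47.1 | 43.6 / 50.8 |
| Imbalance ≥10 points for AAT | 54.6 / 46.8 | 58.3 / 50.1 |

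Stratifying gains 7.4 or 7.2 points in one tail and gives up 7.8 or 8.2 in the other. Weighted by 12%, the tails net to 0.12×(7.4-7.8) = -0.05 and 0.12×(7.2-8.2) = -0.12 points.

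**5. Average change in power from stratifying, by prognostic strength (treatment hazard ratio 0.6).**

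| Risk contrast | Change, points |
|---|---|
| None (38% in both groups), survival | about -0.5 |
| 1.24 (Table 1-1 without liver rows), survival | -0.1 to -0.2 |
| 1.43 (Table 1-1), survival, 0-15% relapse deaths | +0.1 to +0.5 |
| 2.33 (general cohort), all three endpoints | +1.8 to +3.0 |

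With 4-5% of trials discordant, the simulation error of a difference is about √(0.045/40,000) = 0.1 points, so the two middle rows are close to zero. At Table 1-1 rates NRM and PFS also barely change: NRM 47.1-54.7% against 47.2-54.9%, PFS 37.6-50.9% against 37.7-51.2%.

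**6. Error rate.** With no treatment effect, one-sided error over all three endpoints is 2.4-2.8% for both tests. Given an imbalance of 10 points or more favouring AAT it is 3.4-4.4% unstratified against 2.2-2.9% stratified. Given one against AAT it is 1.2-2.0% against 2.2-3.0%. The two directions offset, and familywise control is intact.

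**7. How often would the choice matter?** At Table 1-1 rates the unstratified test alone rejects in 1.9-2.4% of trials and the stratified test alone in 2.2-2.6%. Steps 4 to 6 are reached only after steps 1 to 3 succeed. Assuming 50-70% of responders have a duration-of-response event and a hazard ratio of 0.5-0.6, Day 28 response and one duration test both succeed in about 29-57% of trials. If discordance is unrelated to passing, the choice matters in 0.04×0.29 = 1.2% to 0.05×0.57 = 2.9% of trials.

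**The case for a change.** The best case for stratifying is conditional and does not rest on average power. Once the arms are seen to differ by 10 points or more in high-risk share, the unstratified survival test has lost or gained about 7 to 8 points of power, while the stratified test has hardly moved. Against a worst-case cost of about half a point, that is cheap insurance for a confirmatory claim. The covariate needs no new data, and SAP section 1 allows revisions before the hard lock.

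The conditional figures stand. Four things limit what follows from them.

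- The argument applies to any prognostic baseline factor. Validity rests on randomization, and the unconditional error rate is correct.
- Imbalance would not go unnoticed. SAP 7.2.1 tabulates Minnesota risk at baseline, and SAP 7.5.2 to 7.5.4 already provide risk-adjusted hazard ratios with confidence intervals. Stratified tests added as sensitivity analyses would contribute almost nothing more.
- The change would be partial. It stratifies on a factor not used in the randomization and leaves out center, which was used and which Protocol 5.1.2 expects to matter more. It also leaves unadjusted the duration-of-response tests that decide whether steps 4 to 6 are reached.
- It would move three confirmatory tests away from those named in the protocol, late in the trial, for an average gain near zero.

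**Conclusion.** The concern does not hold. The unstratified tests are valid, agree with the protocol and keep their level. On the documents' own prognostic contrast, stratifying by Minnesota risk changes average power by between about -0.2 and +0.5 points, and the sign depends on whether the liver rows of Table 1-1 are included. Only the general-cohort contrast, which overstates the difference among enrolled patients, gives 2 to 3 points. Reasonable statisticians could choose either test, and the adjusted Cox models already cover the case of a visible imbalance.

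This rests on an assumed treatment hazard ratio of 0.6, assumed relapse and relapse-death rates, and a high-risk share between 35% (Protocol 5.3.2.1) and 65% (SAP 4.3). Those two shares disagree, but the conclusion is the same at both. Table 1-1 covers lower-GI presentations only and gives NRM, not all-cause mortality. A contrast among enrolled patients near 2.33 would make stratifying worth more, but would not make the planned tests wrong.

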7.5.4 PROGRESSION-FREE SURVIVAL (PFS)

PFS is defined as being alive and free of relapse/progression of the primary disease. The time from randomization until PFS failure will be described in the ITT population graphically for each treatment arm using the Kaplan-Meier estimator, with numbers of subjects at risk at specific time points presented for each treatment group. Estimates of PFS at 6 and 12 months post-randomization will be provided along with 95% CIs computed using the complementary log-log transformation as detailed in Kalbfleisch and Prentice 1980. For the primary analysis, the log-rank test will be used to compare PFS within 12 months post-randomization between arms as the primary analysis. **Table 22** shows the estimand for PFS. The clinical question of interest is: what is the difference in PFS between AAT combined with corticosteroids versus PTM combined with corticosteroids in patients with high risk acute GVHD following allogeneic HSCT, regardless of discontinuation of study treatment?

Table 22: Estimand for Progression-free Survival

Estimand Attribute	Definition		
Variable	Progression-free Survival, refer to Sections 6.3.4 and 7.9 for details		
Treatment	AAT (+corticosteroids) or PTM (+corticosteroids), refer to Section 2.1 for details		
Population	Patients with high risk acute GVHD following allogeneic HSCT		
Intercurrent Events	Event	Strategy	Description
	1. Death	Composite strategy	Classified as an event
	2. Relapse / progression	Composite strategy	Classified as an event
	3. Discontinuation of study treatment	Treatment policy	No effect on variable

Estimand Attribute	Definition
Population-level Summary	PFS probabilities at 6 and 12 months with CIs for each arm; log rank test p-value comparing arms from randomization to 12 months post-randomization

In a supplementary analysis, a Cox proportional hazards model with mixed effects will be used to compare PFS between treatment arms while adjusting for an MN risk fixed effect and center-group lognormal frailties. The Cox regression model will be used to evaluate the adjusted hazard ratio of treatment (AAT vs. PTM) using a point estimate and a 95% CI.

